8. Has an active autoimmune disease requiring systemic treatment within the past 3 months or a documented history of clinically severe autoimmune disease, or a syndrome that requires systemic steroids or immunosuppressive agents. Subjects with vitiligo or resolved childhood asthma/atopy would be an exception to this rule. Subjects that require intermittent use of bronchodilators or local steroid injections would not be excluded from the study. Subjects with hypothyroidism stable on hormone replacement or Sjorgen's syndrome will not be excluded from the study.
9. Has evidence of interstitial lung disease or active, non-infectious pneumonitis, active or prior documented inflammatory bowel diseases (e.g., Crohn's disease, ulcerative colitis)
10. Has an active infection requiring systemic therapy. Prior to dosing with study drug(s), the subject must be at least 5 half-lives from their last dose of antibiotic.
11. Has a history or current evidence of any condition, therapy, or laboratory abnormality that might confound the results of the trial, interfere with the subject's participation for the full duration of the trial, or is not in the best interest of the subject to participate, in the opinion of the treating investigator.

12. Has known psychiatric or substance abuse disorders that would interfere with cooperation with the requirements of the trial.
13. Has a known history of human immunodeficiency virus (HIV) (HIV 1/2 antibodies).
14. Has known active hepatitis B (e.g., HBsAg reactive) or hepatitis C (e.g., HCV RNA [qualitative] is detected).
15. Has irreversible toxicity that may be exacerbated by study drugs. However, irreversible toxicity that is not reasonably expected to be exacerbated by study drug(s) may be included (e.g., hearing loss) after consultation with the sponsor medical monitor.
16. Has a contraindication to administration of [REDACTED]
[REDACTED]
[REDACTED]
17. Has a known allergy to any component of the study drug(s) formulations.
18. Has contraindication to administration of non-steroidal anti-inflammatory drugs (NSAIDs).
19. Has a major surgical procedure (as defined by the investigator) within 30 days prior to the first dose of study drug(s) or still recovering from prior surgery.
 - Note: If subject received major surgery, they must have recovered adequately from the toxicity and/or complications from the intervention prior to starting therapy at the discretion of the Investigator.
20. Has received a live vaccine within 30 days prior to the first dose of trial treatment.
21. In the opinion of the investigator, has rapidly progressing disease, OR has life expectancy of less than 6 months, OR would be unable to receive at least 1 cycle of therapy.

22. Has uncontrolled intercurrent illness including, but not limited to, ongoing or active infection, symptomatic congestive heart failure, uncontrolled hypertension, unstable angina pectoris, cardiac arrhythmia, active peptic ulcer disease or gastritis, or psychiatric illness/social situations that would limit compliance with study requirement, substantially increase risk of incurring AEs from MEDI4736 or compromise the ability of the subject to give written informed consent.

23. Has a history of idiopathic pulmonary fibrosis (including pneumonitis), drug-induced pneumonitis, organizing pneumonia, risk of pulmonary toxicity, or evidence of active pneumonitis on screening chest CT scan.

5.2 Trial Treatments

The treatments to be used in this trial are outlined below in [Table 2](#). Trial treatment should begin on the day of randomization or as close as possible to the date on which treatment is allocated/assigned.

Table 2 Trial Treatment

Drug	Dose	Route of Administration	Regimen
Part A (Combination therapy)			
ADXS11-001	1 x 10 ⁹ (fixed)	IV infusion	Q4W
MEDI4736 ^a	3 mg/kg (starting dose)	IV infusion	Q2W
Part B			
ADXS11-001 (monotherapy)	1 x 10 ⁹ (fixed)	IV infusion	Q4W
MEDI4736 (monotherapy)	10 mg/kg	IV infusion	Q2W
Combination	RP2D	IV infusion	Q2W

^a In Phase 1, the MEDI4736 3 mg/kg starting dose will be escalated/de-escalated to determine a recommended dose for Phase 2 combination therapy; in Phase 2, the MEDI4736 monotherapy dose will be 10 mg/kg

5.2.1 Dose Selection/Modification

5.2.1.1 Dose Selection

[figure not shown]
The rationale for selection of doses to be used in this trial is provided in Section [4.2.3 – Rationale for Dose Selection](#).

Details on the dose calculation, preparation and administration are provided in the Pharmacy Manual. Dose levels to be explored in Part A are shown below.

Dose Level	ADX11-001	MEDI4736
1	1×10^9 cfu (Q4wks)	3 mg/kg (Q2wks)
2	1×10^9 cfu (Q4wks)	10 mg/kg (Q2wks)
-1	1×10^9 cfu (Q4wks)	1 mg/kg (Q2wks)

Part A of the study is a Phase 1 3+3 design of ADXS11-001 and MEDI4736 combination therapy. MEDI4736 and ADXS11-001 will be administered in sequential cohorts of 3-6 subjects with a minimum of 48 hours between initial dosing for each of the first 3 subjects enrolled in the study. The first cohort will enroll a minimum of 3 subjects according to a standard 3+3 design shown schematically below.

Figure 1 3 + 3 Design Schematic

- Subjects in the first cohort will receive a dose of MEDI4736 at 3 mg/kg and ADXS11-001 1×10^9 cfu (Dose Level 1).

- If no DLTs are experienced, the next dose level of ADXS11-001 1×10^9 cfu + MEDI4736 at 10 mg/kg (Dose Level 2) will be explored.
- If 1 DLT is experienced, 3 additional subjects will be enrolled. If there is 1 DLT among 6 subjects, the next dose level will be explored.
- If ≥ 2 DLTs are observed in the first dose cohort, the starting dose of MEDI4736 will be de-escalated to 1 mg/kg and a dose de-escalation cohort will be enrolled (Dose Level -1).

All decisions regarding dose escalation or de-escalation will be guided by the 3+3 study design and will be made by the sponsor in consultation with investigators. The sponsor reserves the right to expand the number of subjects in each of the cohorts to better evaluate safety and tolerability, and to evaluate other doses.

The dose that will be utilized in Part B will be the highest maximal dose level evaluated in Part A that has an observed DLT rate of $<33\%$.

Dose escalation/de-escalation decisions for MEDI4736 will use pre-defined DLT criteria (Section 5.2.1.1 – Dose Limiting Toxicities). Subjects who complete the DLT period may dose-escalate to the RP2D if approved by the sponsor.

5.2.1.2 Dose Limiting Toxicities

Dose-limiting toxicities will be evaluated during the Phase 1 combination dose-determination phase. All toxicities will be graded using NCI CTCAE v 4.03. The period for evaluating DLT will be from the first dose of investigational product through 28 days post initial dose for each subject. The occurrence of any of the following will be considered a DLT, if judged by the investigator to be possibly, probably or definitely related to combination therapy.

1. Any \geq Grade 4 irAE
2. Any \geq Grade 3 colitis
3. Any \geq Grade 3 non-infectious pneumonitis irrespective of duration

4. Any Grade 3 irAE, excluding colitis or pneumonitis, that does not downgrade to Grade 2 within 3 days after onset of the event despite optimal medical management including systemic corticosteroids or does not downgrade to \leq Grade 1 or baseline within 14 days of AE onset
5. Liver transaminase elevation $\geq 5x$ but $\leq 8x$ ULN that does not downgrade to Grade 2 within 5 days after onset with optimal medical management, including systemic corticosteroids. Transaminase elevation $>8x$ ULN or total bilirubin $>5x$ ULN will be considered a DLT regardless of duration or reversibility.
6. Any increase in AST or ALT $>3x$ ULN and concurrent increase in total bilirubin $>2x$ ULN (Hy's Law).
7. Bacterial meningitis documented by symptoms and confirmed by lumbar puncture culture results
8. Listeremia: persistent (for 48-72 hours) symptoms consistent with listeremia (e.g., fever and muscle aches, often preceded by diarrhea or other gastrointestinal symptoms)
9. \geq Grade 3 flu-like symptoms or cytokine release syndrome symptoms that persist for >24 hours after study drug administration despite symptomatic treatment.
10. \geq Grade 2 allergic reaction (not due to antibiotic): will receive no further doses.
11. Any drug-related “non-irAE” \geq Grade 3 except for the exclusions listed below.
 - Grade 3 fatigue for ≤ 7 days
 - Grade 3 endocrine disorder (thyroid, pituitary, and/or adrenal insufficiency) that is managed with or without systemic corticosteroid therapy and/or hormone replacement therapy and the subject is asymptomatic.
 - Grade 3 inflammatory reaction attributed to a local antitumor response (e.g., inflammatory reaction at sites of metastatic disease, lymph nodes, etc.).

- Concurrent vitiligo or alopecia of any AE grade
- Grade 3 infusion-related reaction that resolves within 6 hours with appropriate clinical management.
- Grade 3 or Grade 4 neutropenia that is not associated with fever or systemic infection that improves by at least 1 grade within 3 days. Grade 3 or Grade 4 febrile neutropenia will be a DLT regardless of duration or reversibility.
- Grade 3 or Grade 4 lymphopenia.
- Grade 3 thrombocytopenia that is not associated with clinically significant bleeding that requires medical intervention, and improves by at least 1 grade within 3 days.
- Isolated Grade 3 electrolyte abnormalities that are not associated with clinical signs or symptoms and are reversed with appropriate maximal medical intervention within 3 days.

irAEs are defined as AEs of immune nature (i.e., inflammatory) in the absence of a clear alternative etiology. In the absence of clinical abnormality, repeat laboratory testing will be conducted to confirm significant laboratory findings prior to designation as a DLT. While the rules for adjudicating DLTs in the context of dose escalation are specified above, an AE not listed above may be defined as a DLT after consultation with the sponsor and investigators, based on the emerging safety profile.

5.2.1.3 Treatment Modification

In Part A, dose escalation/de-escalation for MEDI4736 in the combination will be based on defined DLT criteria (Section 5.2.1.1); the ADXS11-001 combination therapy dose is 1×10^9 cfu (fixed). In the event of DLT, the investigator will determine relatedness to the study treatment combination.

With ADXS11-001 treatment, a clear pattern of treatment-related AEs consistent with cytokine release has emerged consisting of transient Grade 1 or 2 (mild-moderate) flu-like or cytokine release syndrome symptoms (such as chills, nausea and vomiting), the majority of which occur within the first 6 hours after infusion (see also Section 5.6.1). Symptoms either self-resolve or respond quickly to symptomatic treatment. There has been no evidence of listeriosis, no persistent symptoms, no delayed symptoms, and no evidence of cumulative

toxicity in subsequent doses. Treatment modification guidelines for cytokine release syndrome symptoms are shown in [Table 3](#). Treatment modification guidelines for irAEs are shown in [Table 4](#) below.

Table 3 Treatment Modification Guidelines for ADXS11-001 Cytokine Release Syndrome symptoms

Toxicity	Grade	Modification
1st episode of symptoms associated with CRS (e.g. Nausea, vomiting, chills, rigors, hypotension, fever)	1-2	No modification on subsequent ADXS11-001 infusion
	3-4	
Extend infusion time [REDACTED][REDACTED]Consider increasing prophylaxis dose of NSAIDSConsider incorporating pretreatment fluids to manage hypotension.
Second episode of CRS	1-2	No modifications
	3	Discussion with sponsor required
	4	If symptoms have not ameliorated from aforementioned modifications, subject should be discontinued from study

Table 4 Dose Modification Guidelines for Immune-related Adverse Events - MEDI4736 Monotherapy and Combination Arms

Severity	Immune-related Adverse Events (irAEs) ^a	All Other Events
Grade 1	None	None
Grade 2	
For endocrinopathy: Hold MEDI4736/Combination dose; do not hold ADXS11-001 (unless during combination therapy). When endocrinopathy is controlled, resume MEDI4736/Combination administration at next scheduled dose.
 
For dermatologic irAEs: MEDI4736/Combination may be dosed at the next scheduled time point.
 
For pneumonitis: Hold MEDI4736/Combination until resolution to \leqGrade 1. If resolution to \leq Grade 1 occurs within 3 days of the initiation of maximal supportive care (including corticosteroids)^b, resume MEDI4736/Combination administration at next scheduled dose. Otherwise, discontinue MEDI4736/Combination.
 
For all other irAEs: Hold MEDI4736/Combination until resolution to \leqGrade 1. If resolution to \leqGrade 1 does not occur within 30 days of irAE onset, discontinue MEDI4736/Combination
	
Hold MEDI4736/Combination until resolution to \leqGrade 1 or baseline. If resolution to \leqGrade 1 does not occur within 30 days, discontinue MEDI4736/Combination

Grade 3	
For endocrinopathy: Hold MEDI4736/Combination dose. When endocrinopathy is controlled, resume MEDI4736/Combination administration at next scheduled dose.
 
For dermatologic irAEs: Hold MEDI4736/Combination until resolution to \leqGrade 1 or baseline. If resolution to \leqGrade 1 or baseline does not occur within 30 days, discontinue MEDI4736/Combination.
 
For elevations in transaminases: For elevations in transaminases up to $8 \times$ ULN, hold MEDI4736/Combination until resolution to \leqGrade 1 or baseline. If elevations downgrade to \leqGrade 2 within 7 days or resolve to \leqGrade 1 or baseline within 14 days of onset, resume MEDI4736/Combination administration at next scheduled dose. Otherwise, discontinue MEDI4736/Combination. For elevations in transaminases $>8 \times$ ULN, discontinue MEDI4736/Combination.
 
For elevations in bilirubin: For elevations in bilirubin up to $5 \times$ ULN, hold MEDI4736/Combination until resolution to \leq Grade 1 or baseline. If elevations downgrade to \leq Grade 2 ($< 3 \times$ ULN) within 7 days or resolve to \leq Grade 1 or baseline within 14 days, resume MEDI4736/Combination administration at next scheduled dose. Otherwise, discontinue MEDI4736.
 
For all other irAEs: Discontinue MEDI4736/Combination.
	
Hold MEDI4736/Combination until resolution to \leqGrade 1 or baseline. For AEs that downgrade to \leqGrade 2 within 7 days or resolve to \leqGrade 1 or baseline within 14 days, resume MEDI4736/Combination administration at next scheduled dose. Otherwise, discontinue MEDI4736/Combination.

Grade 4	Discontinue MEDI4736/Combination.	Discontinue MEDI4736/Combination.

AE = adverse event; irAE = immune-related adverse event; ULN = upper limit of normal.

^a Management of irAEs may require administration of immunosuppressive medications (and/or hormone replacement therapy for endocrinopathies). Resolution of irAEs managed in this manner in the timeframes specified is acceptable.

^b Subjects who require corticosteroids for resolution must have discontinued corticosteroids. Subject can restart study therapy upon resolution of irAE and cessation of corticosteroid treatment for 14 days.

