Platelets	$\geq 75,000 / \text{mcL}$
Hemoglobin	$\geq 9 \text{ g/dL}$ or $\geq 5.6 \text{ mmol/L}$
Renal	
Serum creatinine OR Measured or calculated ^a creatinine clearance (GFR can also be used in place of creatinine or CrCl)	$\leq 1.5 \times$ upper limit of normal (ULN) OR $\geq 50 \text{ mL/min}$ for subject with creatinine levels $> 1.5 \times$ institutional ULN
Hepatic	
Serum total bilirubin	$\leq 1.5 \times$ ULN OR Direct bilirubin \leq ULN for subjects with total bilirubin levels $> 1.5 \text{ ULN}$
AST (SGOT) and ALT (SGPT)	$\leq 2.5 \times$ ULN OR $\leq 5 \times$ ULN for subjects with liver metastases
Coagulation	
International Normalized Ratio (INR) or Prothrombin Time (PT)	$\leq 1.5 \times$ ULN unless subject is receiving anticoagulant therapy as long as PT or INR is within therapeutic range of intended use of anticoagulants
Activated Partial Thromboplastin Time (aPTT)	$\leq 1.5 \times$ ULN unless subject is receiving anticoagulant therapy as long as aPTT is within therapeutic range of intended use of anticoagulants
^a Creatinine clearance should be calculated per institutional standard.	

8. Female subjects of childbearing potential (not surgically sterilized or not free from menses for > 1 year):
 - a. must have a negative urine or serum pregnancy test result within 72 hours prior to receiving the first dose of study medication. If the urine test is positive or cannot be confirmed as negative, a serum pregnancy test will be required.
 - b. must be willing to use 2 methods of birth control through 120 days after the last dose of study treatment (Section 5.7.2).
9. Male subjects must agree to use an adequate method of contraception starting with the first dose of study treatment through 120 days after the last dose of study therapy.

10. Must have a washout period of at least **14** days from completing prior standard of care therapy to the initiation of study therapy. For subjects who have been treated with either prior investigational therapy, including, but not limited to anti-PD-1, anti-PD-L1 or CTLA4 therapy, a washout period of **28** days is required*. (* *If a subject received a therapy where delayed toxicity is a concern or expected (e.g., skin reaction with RT or mucositis with 5FU) then additional wash out should be considered after discussion with the medical monitor.*)

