5.2.2.1 Combination Dosing (Part A & Part B)

For Combination dosing, MEDI4736 will be given Q2W (Weeks 1, 3, 5, and 7 of each 8-week cycle) and ADXS11-001 will be given Q4W (Weeks 1 and 5 of each 8-week cycle). On days when both treatments are administered (Weeks 1 and 5 of each cycle), subjects will first receive the MEDI4736 infusion in 250 mL [REDACTED]

[REDACTED] after end of MEDI4736 infusion, subjects should be premedicated with NSAIDS and oral antiemetics (Section 7.1.4.2). **The ADXS11-001 infusion can begin [REDACTED] after the subject has been premedicated.** When given the same day as MEDI4736, ADXS11-001 will be given *in 100 mL* of normal saline [REDACTED], to reduce the potential for fluid overload.

Any subject administered ADXS11-001 will also receive antibiotics. Specific details of antibiotic regimen are provided in Section 7.1.4.2.

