7.1.2.14.1 Laboratory Safety Evaluations (Hematology, Chemistry and Urinalysis)

Laboratory tests for hematology, chemistry, urinalysis, and others are specified in **Table 9**.

The total amount of blood/tissue to be drawn/collected over the course of the trial (from pre-trial to post-trial visits), including approximate blood/tissue volumes drawn/collected by visit and by sample type per subject can be found in the Laboratory Manual.

Subjects must meet all lab criteria prior to dosing. Laboratory tests can be performed no more than 3 days prior to dosing. If screening laboratory tests are performed within 5 days prior to initial study treatment, they can be used for C1D1 labs. Results must be reviewed by the investigator or qualified designee and found to be acceptable prior to each dose of trial treatment.

Table 9 Laboratory Tests

Hematology	Chemistry	Urinalysis	Other
Hematocrit	Albumin	Blood	Serum β-human chorionic gonadotropin†
Hemoglobin	Alkaline phosphatase	Glucose	(β-hCG)†
Platelet count	Alanine aminotransferase (ALT)	Protein	PT (INR)
WBC (total and differential)	Aspartate aminotransferase (AST)	Specific gravity	aPTT
Red Blood Cell Count	Lactate dehydrogenase (LDH)	Microscopic exam (If abnormal results are noted)	Total triiodothyronine (T3)
Absolute Neutrophil Count	Carbon Dioxide ‡ (CO₂ or bicarbonate)	Urine pregnancy test †	Free tyroxine (T4)
	Creatinine		Thyroid stimulating hormone (TSH)
	Calcium		PK
	Chloride		
	Glucose		Blood for correlative studies
	Potassium		
	Sodium		
	Total Bilirubin		
	Direct Bilirubin (If total bilirubin is elevated above the upper limit of normal)		
	Total protein		
	Blood Urea Nitrogen		

† Perform on women of childbearing potential only. If urine pregnancy results cannot be confirmed as negative, a serum pregnancy test will be required.

‡ If considered standard of care in your region.

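### Table 4's Grade 3 bilirubin line stops only MEDI4736 when its recovery window is missed, so combination subjects have no bilirubin-specific permanent stop for ADXS11-001

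*Combined protocol and SAP*

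**What the plan says.** Table 4 in Section 5.2.1.3 is titled "Dose Modification Guidelines for Immune-related Adverse Events - MEDI4736 Monotherapy and Combination Arms". Its orders are addressed to MEDI4736/Combination, so one wording serves both kinds of arm.

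The Grade 3 immune-related cell has separate lines for transaminases and for bilirubin. Both begin with the same hold order: "ULN, hold MEDI4736/Combination until resolution to" Grade 1 or baseline. Both allow dosing to resume if the value falls to Grade 2 or below within 7 days, or to Grade 1 or baseline within 14 days. They differ in what happens when neither window is met:

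- Transaminases: "within 14 days of onset, resume MEDI4736/Combination administration at next scheduled dose. Otherwise, discontinue MEDI4736/Combination".
- Bilirubin (up to 5 x ULN): "within 14 days, resume MEDI4736/Combination administration at next scheduled dose. Otherwise, discontinue MEDI4736". The line ends there.

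The Grade 3 cell in the All Other Events column, with the same windows, reads "within 14 days, resume MEDI4736/Combination administration at next scheduled dose. Otherwise, discontinue MEDI4736/Combination".

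Section 5.2.2.1 sets the combination schedule: "ADXS11-001 will be given Q4W (Weeks 1 and 5 of each 8-week cycle"), with MEDI4736 every 2 weeks. Section 7.1.2.14.1 adds a general condition: "Subjects must meet all lab criteria prior to dosing".

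**The concern.** In the combination arms the word after the slash carries an order beyond MEDI4736 to the whole regimen. The bilirubin line uses it for the hold and for the resumption, then drops it for the permanent stop. A site that follows the table as written would end MEDI4736 and find no matching instruction for ADXS11-001.

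What is at stake is consistent safety conduct. After a liver event that fails the protocol's own recovery window, a permanent stop of ADXS11-001 would depend on which analyte was slow to recover. For the same bilirubin course, it would also depend on whether the investigator called the event immune-related. The trial is open-label and multicenter and has no external data safety monitoring committee (Section 8.2), so the table's wording is what sites will apply.

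**Working it through.** No power or error-rate calculation is involved. The check is a count of Table 4's orders, a side-by-side reading and a dated example.

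**1. Count of dosing orders in Table 4.** The remark on ADXS11-001 in the Grade 2 endocrinopathy line is not counted as a separate order.

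| Order | Grade 2 | Grade 3 | Grade 4 | Total | Extends to the combination |
|---|---|---|---|---|---|
| Hold | 4 | 5 | 0 | 9 | 9 |
| Resume | 2 | 4 | 0 | 6 | 6 |
| May be dosed | 1 | 0 | 0 | 1 | 1 |
| Discontinue | 3 | 6 | 2 | 11 | 10 |
| All | 10 | 15 | 2 | 27 | 26 |

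The 11 discontinue orders are:

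- Grade 2: pneumonitis 1, other immune-related events 1, all other events 1.
- Grade 3: dermatologic 1, transaminases 2, bilirubin 1, other immune-related events 1, all other events 1.
- Grade 4: one in each column.

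3 + 6 + 2 = 11, and 11 - 10 = 1. The one exception is Grade 3 bilirubin.

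**2. The three Grade 3 rules that share the same windows.**

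| Rule | Held | Resumed if a window is met | Stopped if both are missed |
|---|---|---|---|
| Transaminases, immune-related, up to 8 x ULN | MEDI4736/Combination | MEDI4736/Combination | MEDI4736/Combination |
| Bilirubin, immune-related, up to 5 x ULN | MEDI4736/Combination | MEDI4736/Combination | MEDI4736 only |
| All Other Events | MEDI4736/Combination | MEDI4736/Combination | MEDI4736/Combination |

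**3. Other rules that might supply the stop.**

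- Table 3 covers cytokine release symptoms only.
- The dose-limiting toxicity list (Section 5.2.1.2) can classify such an event as a DLT in Part A, but only its allergic-reaction item ends dosing for the subject.
- Section 7.1.2.14.1 withholds a dose while laboratory values are out of range; it is not a permanent stop. I take the criteria it refers to as those of Table 1: total bilirubin up to 1.5 x ULN, or direct bilirubin no higher than "ULN for subjects with total bilirubin levels" above that limit.
- Section 5.8 requires study treatment to stop for unacceptable adverse experiences or when the investigator so decides. It applies here, but it has no bilirubin threshold or time window.

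**4. Dated example.** The values are invented to show the logic. The subject is in a combination arm, transaminases are normal, the event is judged immune-related, and the windows are counted from onset (an assumption, because the bilirubin line does not give a starting point).

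- Day 15 (Week 3): bilirubin 4 x ULN. The combination is held.
- Day 15 + 7 = Day 22: 3.5 x ULN. Table 4 puts Grade 2 below 3 x ULN, so the first window is missed.
- Day 15 + 14 = Day 29: 3.2 x ULN. The second window is missed and MEDI4736 is discontinued. ADXS11-001, due that day, stays on hold.
- Day 57 (Cycle 2 Week 1; the Q4W schedule gives Days 1, 29 and 57): 1.0 x ULN. The hold has ended and Table 1 is met. Nothing in Table 4 now stops ADXS11-001; only Section 5.8 could.

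**5. Subjects under the rule.** Part B randomizes 48 subjects 1:1:2, so 48 x 2/4 = 24 receive the combination. Part A adds 6 to 18. 24 + 6 = 30 and 24 + 18 = 42. This is everyone to whom the line could apply, not the number affected.

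**The case against.** The strongest reply is that context fills the gap. Table 2 lists the combination as one Part B treatment, Section 2.2 bars crossover to another arm, and no section describes ADXS11-001 alone for a combination subject. The only ADXS11-001 remark in Table 4 (Grade 2 endocrinopathy) has it held along with MEDI4736 during combination therapy. On this view a word was dropped and a careful site would stop both drugs. This is probably how the line arose. It does not settle the matter, because no text forbids continuing one component, and if stopping MEDI4736 always ended the combination, the added word in the other ten orders would be redundant.

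A second reply is that stopping only MEDI4736 may be reasonable. Section 4.2.3.1 says ADXS11-001 has not been linked to delayed or autoimmune symptoms, and Section 7.2.3.2 links raised transaminases to anti-PD-L1 treatment. That gives some support for treating immune-related liver events differently from others. It cannot explain why the transaminase line stops both drugs and the bilirubin line does not.

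A third reply is that the exposure is small. This stands. It takes an immune-related Grade 3 bilirubin rise, both windows missed, later recovery, and an investigator who restarts ADXS11-001 alone.

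A reader might also infer that Table 4 contradicts itself when transaminases and bilirubin are both Grade 3 and only one recovers in time. The documents do not show a defect there. The unrecovered analyte keeps its own hold, and the pre-dose laboratory rule blocks dosing; by the time that hold could lift, that analyte's discontinue order has already applied. Nothing says that a resume clause for one analyte revives a drug discontinued for the other.

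**Conclusion.** The point holds as an inconsistency in an operative dosing rule. One of 11 discontinue orders omits the combination, against that line's own hold and resume clauses and against two rules with the same windows. Its consequence is the absence of a bilirubin-specific permanent stop for ADXS11-001 in combination subjects who miss the window.

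A reader might infer more: that ADXS11-001 has no permanent stop at all, or that the line orders its restart. Neither is supported. Section 5.8 still requires study treatment to end for unacceptable adverse experiences or on the investigator's decision. The line leaves ADXS11-001 on a hold until Grade 1 or baseline, followed by the pre-dose laboratory criteria. The exposure is therefore confined to late recoverers.

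The rule covers 30 to 42 planned combination subjects. The number affected would be far smaller; the documents give no incidence and I assume none. No endpoint, sample size or analysis is touched. The conclusion rests on reading the line literally and on taking Table 1 as the pre-dose laboratory criteria.

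**What to change.** End the Grade 3 bilirubin line in Table 4 with: *Otherwise, discontinue MEDI4736/Combination.* All 11 discontinue orders would then extend to the combination. If the sponsor does intend ADXS11-001 to continue alone after late recovery, the table should say so and give the reason.

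A sentence stating that the most restrictive instruction governs when several lines apply would be optional tidying; this point does not depend on it.

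The cost is one word in an amendment, with no added tests or visits. The downside is small: a few combination subjects who might have resumed ADXS11-001 alone after late recovery would stop.
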